# 4.5.4 Safety data

All safety analyses will be performed by actual treatment group in the Safety Set.

## 4.5.4.1 Adverse events

The Adverse events (AEs) were reported with the following information: Description, Visit number when AE was reported, Dose of study drug when AE occurred (10 mg, 20 mg, 40 mg, NA), Date of onset or worsening and end date or ongoing, Intensity (mild, moderate, severe), Frequency (once, intermittent and number and period, continuous, unknown), Action taken with studied drug (none, dose modification, temporary interruption, discontinued), Action taken with event (none, corrective treatment, additional exploration, hospitalization  $\leq$  24 hr, hospitalization > 24 hr), Serious adverse event (SAE) (yes, no), Outcome (recovered, recovered with sequelae, worsened, not yet recovered, death), Imputability (likely related, possibly related, unlikely related), Etiology (studied drug, concomitant treatment, associated disease, other, unknown)

Number of events, number and percentage of patients reporting at least one event, presented by primary system organ class (SOC) and preferred term (PT), over the period V2-V8, will be provided for:

- AE
- Serious AE,

- Treatment emergent AE (TEAE), Treatment emergent AE (TEAE) during the stable dose period, TEAE leading to IMP withdrawal, TEAE related to IMP, serious TEAE, severe TEAE, non-serious TEAE (EUDRACT), Treatment emergent fatal AE.
- Special Interest TEAE (SITEAE).

TEAE also will be described according to the intensity, dose in the stable dose period and outcome.

In case a same patient presented the same AE (i.e. same AE as defined according to SOC and PT) several times during the study, only one occurrence per patient will be reported, but the total number of events will be given.

In addition, only TEAEs with incidence >5% (i.e. % of patients with >5 % for a given PT in at least one treatment group) will be presented by SOC and PT in the SAF population.

A listing with all the individual AEs with the associated information will be provided.

# 4.5.4.2 Vital signs

#### **Definition:**

The following vital signs and clinical examination will be analysed during the study:

- Weight (kg)
- BMI (kg/m^2)
- SBP (mmHg)
- DBP (mmHg)
- heart rate (bpm)

For the description of the values at each planned post-baseline visit, in case of retest, only the first analysable one measured at the visit is taken into account.

#### Analysis:

They will be described, in terms of value at baseline, value at each post-baseline visit as well as in terms of change from baseline for SBP, DBP and heart rate.

Moreover, BMI will be described by class calculated by the World Health Organization (2007): underweight: < -2SD; normal range: [-2SD; +1 SD]; Overweight:] +1SD; +2SD] and obese: > +2SD, taking into account the last post-baseline value in regard to baseline state.

## 4.5.4.3 Laboratory evaluations

The laboratory parameters will not be performed by a central laboratory, so quantitative analysis are not possible.

A full laboratory test was performed at screening (V1), at the final double-blind treatment phase evaluation visit (V7) and at early withdrawal visit. Blood samples will be collected and all laboratory tests will be performed according to the Good Laboratory Practice (OECD GLP Principles) by site-dependent Laboratory. The results of laboratory tests will be interpreted by the investigator. Laboratory abnormalities will be defined as laboratory test results that are outside the reference range as defined by the normal range from the testing laboratory. Clinically significant abnormal value at V1 will be determined by the investigator and will exclude patients from study participation. The results of abnormal values of laboratory tests will be reported in the CRF beside the normal range

value given by the testing laboratory, the original document containing all the tested values will be kept in the patient study file.

- Hematology: Red Blood Cells, White Blood Cells (differential count, absolute value), hemoglobin, haematocrit, Mean corpuscular volume (MCV), platelet count.

- Biochemistry: sodium, potassium, chloride, creatinine, alkaline phosphatases, urea, alanine aminotransferase (ALAT), aspartate aminotransferase (ASAT), gamma glutamyl transpeptidase (GGT), total bilirubin, glucose, triglycerides, total cholesterol and prothrombine ratio.

- Laboratory parameters will be analysed by abnormality and by clinically significance of the abnormality (number and percentage of patients in each class)
- A listing of patients with at least one clinically significant abnormality will be provided.

A description in term of status (Positive or Negative) will be computed for the following parameters: - Only for pubescent female a Serum Pregnancy test ( $\beta$ -hCG) will be described.

- Urinalysis: semi-quantitative ("dipstick") analysis for pH, ketone bodies, proteins, glucose, blood.

- Urine drug testing: test of abuse of drugs will be performed on urine samples from 12 years. Screened drugs are amphetamines, barbiturates, benzodiazepines, cannabinoids (THC) and Opioids.

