3.3.2. Secondary endpoints

As secondary endpoints the study will assess efficacy and safety endpoints in pitolisant and placebo groups:

- Changes in EDS as measured by the maintenance of wakefulness test (MWT) between baseline and V7,
- Changes in EDS measured by the Paediatric Daytime Sleepiness Scale (PDSS) between baseline: [V1 score (D-14) + V2 score (D0)]/2 and the end of treatment: [V6 score (D49) + V7 score (D56)]/2,
- Changes in EDS as measured by the Child and Adolescent Sleepiness Scale (CASS) between baseline and the end of treatment.
- Changes in the average number of cataplexy episodes per weeks: (recorded in sleep diary by patient and/or parent/teacher) between the 2 weeks of baseline and the 2 weeks of end study treatment period (V6, V7),
- Differences in weekly frequency of cataplexy episodes (recorded in sleep diary by patient and/or parent/teacher) between baseline and the 4 weeks of stable treatment period (V4 to V7),
- Severity of EDS measured by the clinical Global Impression of severity and change. Changes between baseline and V6, V7,
- Severity of cataplexy measured by the clinical Global Impression of severity and change. Changes between baseline and V6, V7,
- Changes between baseline and V6 will be compared for the TEA-Ch test,
- Comparison between placebo and pitolisant groups on:
 - Withdrawal symptoms questionnaire (DSM IV) on D59 during a phone call (T1) and at the end-of-study visit on D63 (V8) after a one-week period on placebo,
 - Patients' Global Opinion on treatment effect at the end of treatment if able to express

Protocol P11-06/ BF2.649 EudraCT number: 2013-001506-29

himself. If not will be reported either by parents or teachers.

- ,Tolerability as measured by Treatment Emergent Adverse Events (TEAE),
- Changes in Physical examination and Vital signs,
- ECG and calculation of Fridericia's corrected QTc interval (QTcF = $QT/\sqrt{3}\sqrt{60/HR}$),
- Blood laboratory tests (haematology, blood chemistry),
- Mood appraisal adapted to children (CDI and C-SSRS).
- Changes between baseline and at each visit of the open-label period in EDS,
- Safety assessment will be done on monitoring of adverse events, physical examination, vital signs, ECG and Blood Laboratory tests modifications and the mood appraisal throughout the study.

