3.7.2.4. Blood Laboratory tests, urinalysis, urinary drug testing

A full laboratory test should be performed at screening (V1), at the final double-blind treatment

phase evaluation visit (V7) and at early withdrawal visit and during the open-label period at

V10, V13 and all subsequent visits. Blood samples will be collected and all laboratory tests

will be performed according to the Good Laboratory Practice (OECD GLP Principles) by site-

dependent Laboratory. The results of laboratory tests will be interpreted by the investigator.

Laboratory abnormalities will be defined as laboratory test results that are outside the reference

range as defined by the normal range from the testing laboratory. Clinically significant

abnormal value at V1 will be determined by the investigator and will exclude patients from

study participation. The results of abnormal values of laboratory tests will be reported in the

CRF beside the normal range value given by the testing laboratory, the original document

containing all the tested values will be kept in the patient study file.

Blood laboratory test parameters and intra individual changes in these parameters will be

reported and analyzed in all patients.

- Hematology: Red Blood Cells, White Blood Cells (differential count, absolute value),

hemoglobin, haematocrit, Mean corpuscular volume (MCV), platelet count.

- Biochemistry: sodium, potassium, chloride, creatinine, alkaline phosphatases, urea,

alanineaminotransferase (ALAT), aspartate aminotransferase (ASAT), gamma glutamyl

BIOPROJET Version 3.0 Protocol P11-06/ BF2.649 September 30th, 2020

EudraCT number: 2013-001506-29

transpeptidase (GGT), total bilirubin, glucose, triglycerides, total cholesterol, quick time.

- Hormonology: βHCG (only for pubescent female).

- Urinalysis: semi-quantitative ("dipstick") analysis for pH, ketone bodies, proteins, glucose,

blood. If any of these parameters gives a positive result, a quantitative analysis will be

performed to characterize or count: crystals, casts, epithelial cells, white blood cells, red blood

cells and bacteria if required by the investigator.

- Urine drug testing: test of abuse of drugs will be performed on urine samples from 12 years.

Screened drugs are amphetamines, barbiturates, benzodiazepines, cannabinoids (THC) and

Opioids.

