6.1.4. Blood Laboratory tests and Urinalysis

A full laboratory test should be performed at screening visit (V1), at the end of the double blind treatment (V7 or at early withdrawal visit), and at during open-label period at V10, V13, then every 6-month. All laboratory tests will be performed according to the Good Laboratory Practice by site-dependent Laboratory and tests data should be analyzed, reported and duly signed by its responsible. The results of laboratory tests as paper print outs should be reviewed and assessed (dated and signed) by the investigator at the next visit and reported in the specific form of the CRF.

The following blood parameters should be evaluated:

- Hematology: Red Blood Cell Count, White Blood Cell Count including differential (absolute value), Hemoglobin, Haematocrit, Mean corpuscular volume (MCV), Platelet Count (Absolute).
- Biochemistry Tests (Serum/plasma): Sodium (Na), Potassium (K), Chloride (Cl), Creatinine, Alkaline phosphatases, Urea, Alanine aminotransferase (ALAT), Aspartate aminotransferase (ASAT), Gamma-glutamyltranspeptidase (GGT), Total Bilirubin, Blood glucose, triglycerides, total cholesterol, Quick Time.
- β-hCG serum Pregnancy Test should be performed in all pubescent female patients with child-bearing potential. The absence of pregnancy should be confirmed before entering the study.

BIOPROJET Version 3.0 Protocol P11-06/ BF2.649 September 30th, 2020

EudraCT number: 2013-001506-29

All laboratory test results will be coded by using the 3 points scale as following:

- 0 =within the normal limits

- 1 = anomaly but no clinical significant

- 2 = anomaly clinically significant

Results of the clinical laboratory tests performed at screening will be included in the subject's

CRF and considered as baseline values before the product administration.

In addition a semi-quantitative ("dipstick") analysis for pH, ketone bodies, proteins, glucose

and blood should be evaluated. If any of these parameters gives a positive result, a quantitative

analysis will be performed to characterize or count: crystals, casts, epithelial cells, white blood

cells, red blood cells and bacteria if required by the investigator.

Follow-up of laboratory test abnormalities

The best interest of the subjects will always come before that of the trial. Abnormalities of any

laboratory tests considered to represent a significant danger to the subject will lead to immediate

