discontinuation of the drug and the study monitor and Sponsor must be informed immediately.

In the event of abnormalities considered not to represent a danger, continuation of the drug will

be allowed after discussion with the study monitor. These subjects will be followed up with

appropriate medical management until they return to normal or baseline values or clinical

diagnostics of undercurrent illness is confirmed. The results of all known laboratory tests

required by the protocol will be held / recorded in the subject's CRFs. All clinically important

abnormal laboratory tests occurring during the study will be repeated at appropriate intervals

until they return to baseline or to a level deemed acceptable by the investigator and the study

monitor.

6.1.5.

Adverse Events

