# 4.6 Modifications from the statistical section of the protocol

Not Applicable.

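### SAP 4.5.4.3 drops the protocol's within-patient laboratory changes for want of a central laboratory, yet a V1-to-V7 shift table on the protocol's own 0/1/2 code needs no central laboratory

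*SAP*

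**What the plan says.** **Protocol.** Section 3.7.2.4 assigns testing to the site-dependent laboratory and, in the same section, states that "Blood laboratory test parameters and intra individual changes in these parameters will be" reported and analysed in all patients. Section 6.1.4 says "All laboratory test results will be coded by using the 3 points scale as following": 0 for within normal limits, 1 for an anomaly without clinical significance, 2 for a clinically significant anomaly. It sends the screening results to the "CRF and considered as baseline values before the product administration". Section 3.3.2 ends with a safety assessment that covers "vital signs, ECG and Blood Laboratory tests modifications and the mood appraisal throughout the study".

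**SAP.** Section 3.1.2 keeps biological tolerance as an objective. Section 4.5.4.3 repeats most of Protocol 3.7.2.4 but not the sentence on within-patient change. Its reason is: "The laboratory parameters will not be performed by a central laboratory, so quantitative analysis are not possible". The planned output is: "Laboratory parameters will be analysed by abnormality and by clinically significance of the abnormality (number and percentage of patients in each class"), together with a listing of patients who have at least one clinically significant abnormality. No visit, baseline, change or shift is named for the counts.

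**What reaches the CRF.** Protocol 3.7.2.4 and SAP 4.5.4.3 say abnormal values are reported in the CRF beside the local range, with the full report kept in the patient file. Protocol 6.1.4 says the screening results go into the CRF, and that the results of all known tests "required by the protocol will be held / recorded in the subject's CRFs".

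**The concern.** The protocol made its commitment knowing that laboratories were local, so the absence of a central laboratory is not new information that would justify withdrawing it. A baseline has little purpose in a safety analysis unless later results are compared with it.

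The SAP makes such comparisons elsewhere. Section 4.1.5.1 defines baseline and change from baseline for general use. Section 4.5.4.2 plans change from baseline for blood pressure and heart rate, and describes the last post-baseline BMI class against the baseline state. Laboratory classes get neither treatment.

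In the double-blind part, blood is taken only at V1 and at V7 or early withdrawal. That pair is the only placebo-controlled within-patient laboratory comparison in the trial. The samples at V10, V13 and later are open-label and cannot replace it.

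**Working it through.** There is no stated figure to reproduce. The check is a reading of the texts, then a look at what class counts can and cannot show.

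**1. Do local laboratories block a within-patient comparison?** Each result is judged against the testing laboratory's own normal range and then coded 0, 1 or 2 (Protocol 3.7.2.4 and 6.1.4). The code is already relative to the local limits. Crossing a patient's V1 code with the V7 code therefore needs no harmonisation between laboratories. The SAP's reason can apply to pooling raw values; it does not apply to a shift in class.

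**2. What do separate class counts leave open?** For one analyte and one arm, take n patients with both results, a in class 1 at V1 and b in class 1 at V7. Class 2 at V1 excludes the patient, so n − a are in class 0 at V1. The number newly in class 1 at V7 can then be anything from max(0, b − a) to min(b, n − a). Only the cross-tabulation fixes it. The SAP names no visit for the counts, so a may not be reported at all.

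**3. Which transitions are affected?**

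| V1 → V7 | Covered by the SAP text? |
|---|---|
| 0 → 2, 1 → 2 | Largely: class 2 at V1 is excluded, class 2 patients are listed, and clinically significant findings are adverse events |
| 0 → 1 against 1 → 1 | No: both count once in class 1 |
| 1 → 0 | No: recovery is not shown |

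**4. Scale of the counts.** Assume, since the documents give no rate, that a reference range holds 95% of values. With no drug effect, the expected number out of range per analyte is 72 × 0.05 = 3.6 on pitolisant and 36 × 0.05 = 1.8 on placebo. With counts this small, whether one or two patients were already abnormal at V1 matters.

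**5. Why numeric change is worth adding if the data exist.** This is an illustration only. Assumptions not in the documents: a Gaussian analyte, range = mean ± 1.96 SD, a 0.5 SD drift in the active arm only, V1–V7 correlation r of 0.4 to 0.8, two-sided 0.05, and 36 against 72 patients.
- Share out of range with drift: 1 − Φ(1.96 − 0.5) + Φ(−1.96 − 0.5) = 7.9%, against 5.0% without. So 92.1% stay in range.
- Power to compare 5.0% with 7.9%: about 7%.
- Power to compare mean change: SD of change = √(2(1 − r)); SE = SD × √(1/36 + 1/72) = SD × 0.204. For r = 0.4, SE = 1.095 × 0.204 = 0.224, 0.5/0.224 = 2.24, and Φ(2.24 − 1.96) = 61%. For r = 0.6 and 0.8 it is 78% and 97%.
- With a 0.3 SD drift the figures are about 4% against 27–64%; with 0.8 SD, about 20% against 95–100%.

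The SAP plans no laboratory hypothesis test. Power here only measures how much information class counts discard.

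**The case against.** **In-range values may not be in the database.** Under the rule in Protocol 3.7.2.4 and SAP 4.5.4.3, only abnormal values and their ranges are entered. Numeric change could then not be computed for most patients, and the SAP's sentence would be badly explained rather than wrong in effect. This stands, and it is why numeric change must be conditional. It does not touch the shift table, which uses the codes.

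**Nothing guarantees the same laboratory at V1 and V7.** True: it is only likely from site-dependent testing. Codes set against each laboratory's own limits are less exposed to this than raw differences, but not immune.

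**Clinically important findings are already handled.** Largely true. A clinically significant abnormality at V1 excludes the patient. Later ones are listed and are adverse events under Protocol 3.7.2 and 6.1.5.1, where the treatment-emergent definition separates new or worsened events from pre-existing ones. What remains is class 1.

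**The method is open.** Protocol 3.7.2.4 does not say how within-patient changes are to be analysed. A change-of-class table could meet it, and scaling to the reference range is one technique among several. This supports the shift table as the minimum.

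**The table mock-ups are a separate file.** SAP sections 5 and 6 point to it, and it may contain a shift table. It was not available here. The SAP text does not require one.

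**Conclusion.** The point holds in limited form. SAP 4.5.4.3 withdraws a protocol commitment for a reason that does not bear on a within-patient comparison of classes. As written, the SAP does not require persistent class 1 abnormalities to be separated from new ones, in either arm. This is a descriptive safety gap: no efficacy conclusion, error rate or sample size is affected.

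Three stronger readings might be inferred, and the documents do not support them.
- That the SAP cannot tell any new abnormality from a pre-existing one. Class 2 is largely covered, as shown above.
- That numeric change could simply be computed. This depends on in-range values and limits that may not have been captured, and the CRF itself is not available.
- That the entry "Not Applicable" in SAP 4.6 is false. That section concerns the protocol's statistical section, and the dropped sentence is in Protocol 3.7.2.4. The entry is not contradicted, although the departure is declared nowhere else in the SAP.

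The conclusion assumes that the 0/1/2 code is held for each analyte at V1 and at V7 or early withdrawal, as Protocol 6.1.4 implies. The drift figures rest wholly on the assumptions listed with them and are not needed for it.

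**What to change.** 1. In SAP 4.5.4.3, remove the statement that quantitative analysis is not possible.
2. Add, by arm and for each analyte, a shift table of the 0/1/2 code from V1 to V7 or early withdrawal, with the number of patients who have both results.
3. Reconcile Protocol 3.7.2.4 and SAP 4.5.4.3 (abnormal values in the CRF) with Protocol 6.1.4 (screening results and all required results in the CRF).
4. If in-range values and local limits are in the database, also describe change from V1 scaled to the local reference range. If they are not, give that as the reason and declare the departure from Protocol 3.7.2.4.

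**Cost.** Items 1 to 3 need SAP and protocol wording and one extra descriptive table set, with no new data if the codes are held. Item 4 needs data entry only if in-range values were not captured. SAP 4.5.4.3 names 20 blood analytes besides the white-cell differential, so the upper bound is 20 × 2 visits × 108 patients = 4,320 values, plus their limits, from reports already in the patient files.

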## 4.5.4.4 Physical examination

A full physical examination will be performed at screening period (V0 (when applicable) and V1) and at each visit from V2 to V8 (or at early withdrawal visit). Any significant abnormality and change from baseline will be recorded in the CRF and in the source document and will be analyzed as safety parameters. Any significant changes will be reported in the AE pages of the CRF.

A description by visit and by body system of the Physical examination will be provided.

#### 4.5.4.5 Electrocardiogram

ECG will be performed at each visit from the screening visit (V1) to the end of the double blind-phase (V8) or at early withdrawal visit. The main ECG parameters including Fridericia's corrected QTc interval (QTcF =  $QT/^3\sqrt{(60/HR)}$ ) and intra individual changes in these parameters will be reported and analyzed locally

## Definition:

A value is considered as analysable if a non-missing value was obtained from a Sinusal rhythm ECG from the central review (Banook).

For the description of the values at each planned post-baseline visit, in case of retest, only the first analysable one measured at the visit is taken into account.

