3.7.2. Safety criteria

The safety criteria will include:

- Adverse and unexpected events, emergent or not, reported during the study course (frequency, severity, relationship to study drug, incidence and occurrence)
- Change of vital signs parameters (heart rate, blood pressure, body weight) from baseline values

• Physical examination: abnormalities in each system class and change from baseline

• ECG parameters: in particular, calculation of the QTcF value and comparison with the QTcF value of the ECG performed at baseline. If the QTcF is \geq 500 ms or Δ between the QTcF on treatment and the QTcF at baseline is \geq 60 ms, the treatment shall be discontinued and the corresponding ECG forwarded to Bioprojet.

- Laboratory abnormalities (e.g. AEs will be defined as laboratory test results that are outside the reference range as defined by the normal range for laboratory test and clinically signification).
- Occurrence of withdrawal symptoms (to be checked during the phone call at D59 \pm 1 and at V8 end-of-study visit (D63).

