3.7.2.1. Cardiovascular safety: vital signs and ECG

Vital signs including blood pressure, heart rate and body weight will be checked at the each visit.

ECG will be performed at each visit from the screening visit (V1) to the end of the double blind-phase (V8) or at early withdrawal visit and all visits of the open-label period. The main ECG parameters including calculation of Fridericia's corrected QTc interval (QTcF = QT/ 3 \sqrt (60/HR)) and intra individual changes in these parameters will be reported and analyzed locally. If the QTcF value is \geq 500 ms, or if the change from baseline is \geq 60 ms, (observed on two consecutive occasions, i.e. after performing a recheck a few hours later) the treatment shall be discontinued and ECGs (baseline and abnormal ECG) shall be dispatched to Bioprojet.

All ECGs will be reviewed a posteriori by a central reviewer.

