# 4.1.5 Derived variables

## 4.1.5.1 General definitions

The following definitions will be considered:

- Analysable value will be defined as any non-missing value.
- Baseline value will be defined as :
  - For UNS, PDSS and CASS parameters as the mean of V1 and V2 values on condition that values are prior to the first IMP intake (*i.e.* before or the same date as the first IMP intake date). In case of a visit missing value, the baseline will be equal to the non-missing value.
  - For other parameters, the last analysable value prior to the first IMP intake (*i.e.* before or the same date as the first IMP intake date).

Note: In case of patient randomised but not treated over the blind period: value at baseline is defined as the last analysable value prior or equal to the date of randomisation.

- Post-baseline value will be defined as any value recorded at a given timepoint after baseline.
- Change from baseline will be defined as the arithmetic difference between a post-baseline value and the baseline value for a given variable at a given time point.
- End value will be defined only for UNS, PDSS and CASS parameters as :

- The mean of V6 and V7 values. In case of a visit missing value, the End value will be equal to the non-missing value.

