## Analyses:

ECG parameters will be described, in terms of values at baseline, values at each post-baseline visit. Presence of clinically significant ECG abnormalities (yes/no) will be analysed.

ECG parameters will be described, in terms of values at baseline, values at each post-baseline visit. Presence of clinically significant ECG abnormalities (yes/no) will be analysed.

Description of the following binary variables (Yes/No) were also presented:

-QTcF450 =Yes if QTcF post-dose > 450msec

 $-\Delta QTcF = Yes$  if the post-dose versus pre-dose QtcD  $\ge 60$ msec

-QT500 =Yes if the QT post-dose  $\geq$  500 msec

A data list will document individual values for any patient presenting with an abnormal clinically significant value at any time point post dose. Values will be patient ID, first and second reading, treatment, age, gender, and visit.

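### ECG and vital signs use opposite retest rules before and after dosing, and no QTcF flag states its reading or matches the protocol's two-occasion criterion

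*SAP*

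**What the plan says.** **Baseline.** SAP 4.1.5.1 averages V1 and V2 for UNS, PDSS and CASS. Everything else, including ECG and vital signs, follows a different rule: "For other parameters, the last analysable value prior to the first IMP intake".

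**Post-baseline.** SAP 4.5.4.2 (vital signs) and 4.5.4.5 (ECG) use the same sentence for the description of values at each planned visit: "in case of retest, only the first analysable one measured at the visit is taken into account". An ECG value is analysable if a "non-missing value was obtained from a Sinusal rhythm ECG from the central review".

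**What depends on baseline.** SAP 4.5.4.2 describes "change from baseline for SBP, DBP and heart rate". SAP 4.5.4.5 says of the ECG parameters that "intra individual changes in these parameters will be reported and analyzed locally", and it defines a yes/no flag for a QTcF change of at least 60 ms.

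**Flags and listing.** SAP 4.5.4.5 has three flags: QTcF above 450 ms, QTcF change of at least 60 ms, and QT (not QTcF) of at least 500 ms. None names the reading used or asks for confirmation. First and second readings appear together only in a listing "for any patient presenting with an abnormal clinically significant value at any time point post dose".

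**Protocol thresholds.** Section 3.7.2.1 and the synopsis apply QTcF ≥500 ms or a change ≥60 ms when "observed on two consecutive occasions, i.e. after performing a recheck a few hours later". Section 3.7.2 gives the same thresholds and says that "the treatment shall be discontinued and the corresponding ECG forwarded to Bioprojet", without mentioning a recheck.

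**The concern.** A change from baseline is cleanest when both ends are chosen in the same way. Here a repeat taken before dosing replaces the first reading, while a repeat taken after dosing is ignored. If pre-dose repeats are prompted by high values, the repeat tends to fall back towards the child's usual level. The later first readings have had no such correction, so the calculated change is too high in those children.

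The second issue is reporting. In a paediatric trial with QTcF thresholds for stopping treatment, a reader will want the number of children per arm who met those thresholds as the protocol defines them. No planned table gives that number. Because the flags do not name a reading, two programmers could also produce different counts from the same data.

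**Working it through.** The plan gives no figure on this point, so there is none to reproduce. The check has a textual part and an illustration.

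**1. Rules side by side**

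- Retest before dosing: the last value counts (SAP 4.1.5.1).
- Retest at a post-baseline visit: the first value counts (SAP 4.5.4.2 and 4.5.4.5).
- Flags: reading not stated, no confirmation (SAP 4.5.4.5).
- Protocol thresholds of 500 ms and 60 ms: two occasions in 3.7.2.1 and the synopsis; recheck not mentioned in 3.7.2.

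**2. Direction.** Let the first pre-dose reading be b1 = T + e1 and the repeat b2 = T + e2, where T is the child's true level. Compared with using first readings throughout, the mean change moves by

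shift = (share retested) × mean(b1 − b2 among those retested).

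If a high b1 triggers the retest, e1 averages above zero in that group. The error e2 was not selected upward, so the shift is positive.

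**3. Size for QTcF.** All inputs are assumptions: between-child SD 15 ms; a pre-dose retest only if the first reading exceeds 450 ms; entry only if the last pre-dose reading is 450 ms or less; 2,000,000 simulated children per scenario.

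| Mean QTcF (ms) | Within-child SD (ms) | Retested | Shift in mean change (ms) |
|---|---|---|---|
| 400 | 8 | 0.13% | 0.02 |
| 400 | 12 | 0.39% | 0.10 |
| 400 | 20 | 2.03% | 0.87 |
| 420 | 8 | 2.16% | 0.32 |
| 420 | 12 | 4.00% | 0.90 |
| 420 | 20 | 8.73% | 3.22 |

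The effect falls on a few children. In the last row it is 3.22 / 0.0873 = 36.9 ms per retested child.

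**4. Size for systolic pressure.** Assume between-child SD 10 mmHg, reading SD 6 mmHg, and the top 10% of first readings retested. Total variance is 100 + 36 = 136, so total SD is 11.66. The drop in retested children is 1.755 × 11.66 × 36/136 = 5.4 mmHg, where 1.755 is the mean of the top tenth of a standard normal. The arm mean moves by 0.10 × 5.4 = 0.5 mmHg. With no retests it is zero.

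**5. Between arms.** With a true 10 ms drug effect added, the SAP's rule gives 13.89 − 3.89 = 10.00 ms at mean 420, SD 20, and 10.12 − 0.11 = 10.01 ms at mean 400, SD 12. All six scenarios recover 10 ms to within 0.01 ms.

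**6. Flag for change ≥60 ms, no drug effect**

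- One post-baseline visit, within-child SD 20 ms: 1.7 to 1.9% of children on a single reading, about 0.3% confirmed.
- One visit, SD 12 ms: about 0.02% single, less than 0.001% confirmed.
- Six visits sharing one baseline: SD 8 ms, 0.00003% single; SD 12 ms, 0.11% single and 0.004% confirmed; SD 15 ms, 1.2% single and 0.09% confirmed. In 108 children the last pair is 0.012 × 108 = 1.3 and 0.0009 × 108 = 0.1.

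The confirmed figures assume independent errors in readings a few hours apart. Correlated errors would narrow the gap. The ≥500 ms count was not simulated.

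**The case against.** **Both rules are defensible alone.** The last pre-dose value is a common baseline. Taking the first reading after baseline avoids selecting on post-dose retests. This stands: the fault is the mismatch, not either rule.

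**Pre-dose retests may be rare.** No section schedules one. The only recheck described is for a QTcF exceedance on treatment. This stands, and it is why no size can be asserted.

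**A reader might infer that the SAP discards the recheck and that the flags rest on first readings.** The text does not support this. The first-reading rule is worded for the description of values at planned visits, the flags name no reading, and the listing keeps the second reading for some children. The defect is an unspecified derivation and a missing confirmed count.

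**A reader might also apply the recheck to the 450 ms flag.** In the simulation above, at one visit with no drug effect, confirmation would cut that flag from 0.15–10.7% to 0.03–2.6% of children. But the protocol uses 450 ms only as an entry limit, with no recheck, so an unconfirmed count above 450 ms departs from nothing.

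**Confirmed exceedances may surface elsewhere.** Under protocol 3.7.2.1 they lead to discontinuation, and SAP 4.5.1.1 tabulates withdrawal reasons by arm. That helps only in part, because nothing requires those reasons to identify the QTcF threshold. Sites also act on local readings while the SAP uses central ones, so a confirmed count would describe the central data and not audit site decisions.

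**Conclusion.** The concern holds in a limited form. The opposite retest rules are a fact of the text. They push the within-arm change upward in any child retested before dosing for a high value. On mean QTcF this is about 0.02 to 3.2 ms across the assumed scenarios; the documents give neither retest rates nor reading variability, so no single value can be defended.

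It would be tempting to conclude that the drug-placebo comparison is distorted. That does not follow: baseline precedes dosing, the rule is the same in both arms, and the expected shift cancels. Unconfirmed counts lean towards over-reporting, except where a first reading is normal and the repeat is not.

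The reporting gap is the firmer half and needs no assumption: no planned table corresponds to the protocol's two-occasion criterion. How many flags confirmation would remove depends heavily on reading SD, from practically none at 8 ms to about one child in 108 at 15 ms over six visits. This is worth correcting before unblinding, but it does not threaten the trial's conclusions.

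**What to change.** 1. **One retest rule.** Apply the same rule before and after dosing to ECG and vital signs, for example the first analysable reading at V2 as baseline. Averaging V1 and V2 is an optional gain in precision, with the non-missing value used if one is absent. That fallback matters because protocol 5.2.2 says tests done at V0 are not repeated at V1, while the schedule marks vital signs at V1.
2. **Two counts per arm.** Derive QTcF ≥500 ms and change ≥60 ms from all centrally read post-dose ECGs, including rechecks. Report any reading and confirmed on two consecutive readings. Define the 500 ms flag on QTcF, since the SAP currently writes it on QT. Keep the >450 ms flag as an any-reading count.
3. **Fuller listing.** Show both readings for every child with a flagged QTcF, whether or not judged clinically significant.
4. **Protocol consistency.** Section 3.7.2 must be reconciled with 3.7.2.1 and the synopsis on the recheck. Reporting both counts serves either reading meanwhile.

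The cost is SAP wording and a little more programming, with no new visits or measurements. Analysis values may differ by a few ms from the local readings used at site, and the SAP should say so.
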